During a prior appointment, participants are presented with an extensive list of high-caloric salty (potato chips, peanuts) and sweet snack foods (cookies, chocolate), and are asked to select their top three salty and sweet options for a total of six options. During the lab session, participants will be presented with a standardized amount of each of their six preferred high-caloric foods. The snacks will be portioned to 750 calories of each (approximately 4-5 servings of each item). The weight of the food will be assessed at the start and end of each session, and calories consumed will be calculated from baseline evaluations of calories per gram. Each participant will receive the same presentation and amount of food across the two sessions.

Following the presentation of food, participants are then told that they can start eating at any time they wish over the next 3 hours. We model the ability to resist eating over a 3-hour period, to provide sufficient time to capture the effect of the high-caloric snack food triggering eating. Participants are informed that for each minute that they can resist eating, they will receive monetary compensation. The amount of money earned over the 3 hours starts at \$0.35 per minute, and reduces by a penny every 5 minutes. By 180 minutes, the compensation has reduced to \$0 per minute. Participants are provided this information in table format during the laboratory session. If a participant resists eating for the entire 3 hours, they will earn a total of \$31.50. Participants will be videotaped and wear a smartwatch (wearable Biosensor) synced to a research

smartphone during the eating session. The data will be coded and provide information about how fast participants eat and the order in which foods are selected.

When participants can no longer resist and decide to start eating, latency to eat will be recorded in seconds. Participants may eat as much as they wish until the end of the 3-hour ad-lib period. Measures of leptin, ghrelin, food craving, hunger, mood, and vitals will be assessed throughout the laboratory procedure (see **Table 1**). At the end of the period, participants will remain in the laboratory for an additional 1.5 hours to add a response cost if they chose not to consume any food during this period. In other words, they are not immediately able to leave the session to go eat.

**Table 1**: Procedures and assessments for laboratory sessions (also see Table 2).

PERIOD	TIMING	PROCEDURES

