Because the projected effect sizes may not be large enough for detection during interim analyses, we are not proposing a preliminary analysis of accumulating efficacy and safety data by treatment assignment. Instead, we propose to submit semi-annual reports of aggregate data to the DSMB members that contains screening data, baseline demographics, retention data, serious adverse events data, as well as accrual status including projections, times to milestones, and any other data that will help in the assessment of the clinical trial. Based on this report, each DSMB member will complete a form making one of two recommendations: 1) continue recruitment as planned; or 2) schedule formal DSMB meeting immediately. If any DSMB member recommends a meeting, this will be scheduled within one week, minutes will be kept, the report will be

reviewed with the PI, and the committee will vote on whether the study should: 1) continue recruitment unchanged; 2) continue with a protocol amendment; 3) stop recruiting pending further investigation. If, after this meeting, any DSMB member votes to stop recruitment or requests a protocol modification, the Yale IRB will be informed.

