### 13. **Statistical Considerations:** Describe the statistical analyses that support the study design.

Baseline demographic and clinical characteristics for the randomized groups will be compared using chi-square tests for categorical variables, and ANOVA or Kruskal-Wallis tests for continuous variables. Continuous variables will be examined for normality using normal probability plots and Kolmogorov-Smirnov test statistics. If normality is not satisfied, transformations or nonparametric alternatives will be considered. Dropouts and completers will also be compared. Primary analyses will be based on an intent-to-treat basis. Primary outcomes will be tested at the two-sided alpha 0.05 threshold. Secondary analyses will be adjusted for multiple tests using the Bonferroni correction basing the adjustment on the number of conceptually related statistical tests within each hypothesis.

Overall analysis strategy. Mixed-effects models [92] will be used to compare treatments. These models allow for different numbers of observations per subject, use all available data on each subject, and are unaffected by randomly missing data. A further advantage is the capacity to test and account for individual-difference contributions to the treatment outcomes (Cudeck, 1996; Cudeck & Klebe, 2002; Hedeker et al., 1996; Hedeker & Gibbons, 1996; Singer, 1998). They provide flexibility in modeling the correlation structure of the data. In models for each outcome in Aims 1 & 2, we will include obesity status (obese vs. non-obese) and treatment (NB vs. placebo) as between-subject effects, time (see Aim-specific study time points) as a within-subjects factor, and subject as the clustering factor. Across analysis, time-points associated with the 12-week treatment phase will be considered as primary outcomes, and all analyses will be repeated to examine change

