during the 12-month follow-up period. All possible interactions will be modeled and the following primary a priori contrast will be tested: 1) placebo NB vs. active NB. Least-square means will be plotted and compared post-hoc to interpret significant effects. Because we cannot a priori predict the shape of the response over time in each arm of the trial we will first treat time as a categorical predictor and will then test for polynomial trends over time. We will consider different error structures (e.g., AR1, CS, independence) and select the best fitting one based on Schwartz' Bayesian Criterion (BIC). We will compare dropout patterns between groups and if there are concerns of informative dropout or informative intermittent missing data, we will use pattern mixture models [93] to perform sensitivity analyses. Secondary models will include subjects with complete data. To test for assessment reactivity, we will evaluate whether biosensor assessment (yes/no; between-subject variable) moderates our primary outcomes in Aim 1 (as either a main effect, or interacting with medication). If this is found, then all subsequent analyses for Aims 1 & 2 will be limited to the sample (n=140) without the biosensor assessment.

Primary Aim 1. We will use the mixed models described above to test the effectiveness of NB medication for BED patients with and without obesity. The primary aims are to evaluate NB medication for (a) reducing binge eating frequency; and (b) in the patients with obesity, for reducing % weight loss. Significant NB main effects (regardless of obesity status) on frequency of binge eating will be considered supportive of our primary hypothesis. We also expect that NB will be associated with significantly greater reductions in % weight loss among the BED+obese group. In view of the factorial design, we will also be able to assess whether obesity status moderates reductions in binge eating frequency. These analyses will focus on 12-week outcomes. Secondary analysis will be repeated to examine change during the 12-month FU period.

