**Primary Aim 2**. To evaluate potential mechanisms underlying the effect of NB on binge eating behavior, we will first evaluate whether NB treatment changes latency to resist eating, calories consumed, leptin, ghrelin, and food craving employing the mixed models described above. If a potential mechanism demonstrates a significant time x medication effect, we will then evaluate whether improvement in the variable of interest mediates changes in frequency of binge eating over the 12-week treatment period. Following the general analytic framework outlined by Kraemer (2002), we will use the product of the coefficients method to

evaluate the relationship between the mediator, or indirect effect, and outcome. After running a regression equation to determine (1) the effect of treatment on the mediator (provides beta weight for a), we will evaluate (2) the strength of the relationship between the mediator, treatment, and outcome (provides beta b). Using MacKinnon's software PRODCLIN, we will evaluate the asymmetric confidence intervals for the product of the regression estimates (a\*b). Importantly, we note that statistical mediation is not equivalent to causation, and will be sure to appropriately limit our conclusions. Significant NB main effects in latency to resist eating, calories consumed, leptin, ghrelin, and food craving will be considered supportive of our hypothesis. Further, significant mediation of NB-related changes in lab variables on clinical outcomes (reduction in binge eating frequency) will be considered supportive of our hypothesis.

**Exploratory Aim 3**. To account for the hierarchical structure of the data, linear mixed models will be used to assess differences over time in affect and eating behaviors per day collected over a 6-week period. To evaluate potential mechanisms underlying triggers of binge eating behavior, we will first evaluate whether NB treatment changes eating behavior. We will also evaluate the time course of affect and eating behaviors to identify potential antecedents and consequences of binge eating episodes.

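### Latency to eat, capped at 180 minutes, is tested by a time-by-medication (change-score) term; a comparison adjusted for first-session latency with a stated rule for full resisters would be stronger at almost no cost

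*Combined protocol and SAP*

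**What the plan says.** The laboratory procedure (Procedures for Modeling Cue-Induced Eating Behavior) sets a fixed window: "We model the ability to resist eating over a 3-hour period". Participants are paid for each minute they hold out. The outcome is defined only for those who give in: "When participants can no longer resist and decide to start eating, latency to eat will be recorded in seconds". Full resistance is foreseen, since the payment text covers what happens "If a participant resists eating for the entire 3 hours", but no latency value is assigned to that case.

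Section I, item 13 (Statistical Considerations) begins "Mixed-effects models [92] will be used to compare treatments". Primary Aim 2 applies those models to latency together with calories, leptin, ghrelin and craving, asking "whether NB treatment changes latency to resist eating, calories consumed, leptin, ghrelin, and food craving employing the mixed models described above". On covariance, the plan says "We will consider different error structures (e.g., AR1, CS, independence", with the choice made by BIC. Mediation is tested only for a laboratory variable that shows a significant time-by-medication effect. The same paragraph also counts significant drug main effects on these variables as support. The general fallback is "If normality is not satisfied, transformations or nonparametric alternatives will be considered". No censored-data or rank method is named for latency.

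The same procedures section, and the design overview in item 4, allow the first laboratory session to be held at weeks 4–6 of treatment if it cannot be arranged beforehand. The sessions are also optional.

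**The concern.** Two features of latency are not reflected in the planned test.

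- **Change score.** With two sessions per person, the time-by-medication term compares mean change between arms. It carries the full noise of the first session into the comparison instead of using that session as a covariate.
- **Cap.** Values pile up at 180 minutes. Someone who already resists for the full window at the first session cannot show improvement, and no rule says whether such a session is recorded as 180 or left blank. Leaving it blank would remove the participants who resisted best.

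What is at stake is the resisting half of Hypothesis 2.2, which sits under a primary aim, and entry to the mediation step for latency. The number of usable sessions may also fall short of 200, because the sessions are optional and the protocol cites 20–38% attrition in earlier drug trials in this condition.

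**Working it through.** **1. The window.** The payment starts at 35 cents per minute and falls by one cent every 5 minutes. The total is 5 × (35 + 34 + … + 0) = 5 × 630 = 3,150 cents = $31.50, which matches the protocol and confirms the 180-minute cap. There is no power, effect size or SD for latency to reproduce. The safety monitoring plan mentions projected effect sizes ("Because the projected effect sizes may not be large enough for detection during interim analyses") without giving any.

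**2. Inputs.** From the documents: 50 per cell, so 100 per drug arm; 1:1 allocation; two sessions; two-sided 0.05. Assumed: 80 per arm (100 × 0.80, the low end of the cited attrition); between-session correlation ρ of 0.5–0.7; a hazard ratio of 0.65 for starting to eat, or a 0.4 SD shift in latent latency; 20–40% of placebo reaching the cap.

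**3. Baseline adjustment alone, no cap.** Take equal variance σ² at both sessions. Per person, the variance is 2σ²(1 − ρ) for a change score and σ²(1 − ρ²) for ANCOVA. The ratio of ANCOVA to change score is (1 + ρ)/2.

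- ρ = 0.5: ratio 0.75.
- ρ = 0.7: ratio 0.85.

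With a 0.4 SD shift and 80 per arm, z = 0.4 / √(2v/80), where v is the variance above with σ = 1, and power ≈ Φ(z − 1.96).

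| ρ | Change: v, z, power | ANCOVA: v, z, power |
|---|---|---|
| 0.5 | 1.00, 2.53, 72% | 0.75, 2.92, 83% |
| 0.7 | 0.60, 3.27, 90% | 0.51, 3.54, 94% |

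So the change-score test is the weaker one even without a cap. A literal drug main effect averaged over both sessions would be weaker still: its effect is halved and its variance is σ²(1 + ρ)/2, which is equivalent to v = 2(1 + ρ) = 3.0 at ρ = 0.5.

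**4. With the cap.** Simulated power with 100 per arm, ρ = 0.5 and 1,500 trials per scenario (simulation error about 1.3 points). Latent latency is lognormal (log SD 1.2) or normal (SD 70 minutes) with a 0.4 SD shift, or Weibull (shape 0.7) with hazard ratio 0.65.

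| Latency model, placebo at cap | Planned term | ANCOVA on capped latency | Rank ANCOVA |
|---|---|---|---|
| Lognormal, 20% | 0.702 | 0.827 | 0.859 |
| Lognormal, 40% | 0.639 | 0.798 | 0.805 |
| Weibull, 20% | 0.654 | 0.783 | 0.790 |
| Weibull, 40% | 0.489 | 0.620 | 0.665 |
| Normal, 20% | 0.700 | 0.845 | 0.858 |
| Normal, 40% | 0.601 | 0.784 | 0.805 |

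The step from the planned term to ANCOVA, which is baseline adjustment, gains from 12.5 points (0.827 − 0.702) to 18.3 points (0.784 − 0.601). The further step to ranks adds from 0.7 points (0.805 − 0.798) to 4.5 points (0.665 − 0.620). With no true effect, and 20% or 60% at the cap, rejection rates were 4.6–6.3% for the planned term, 5.0–5.5% for ANCOVA and 5.2–5.9% for rank ANCOVA.

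**5. Across the assumed range.** With 80 per arm, the three latency models, 20–40% at the cap and ρ of 0.5–0.7, the gain over the planned term is about 5–20 points for ANCOVA and 6–22 points for rank ANCOVA, both at nominal size.

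**6. Censoring method alone.** Comparing the planned term with a two-session Cox interaction test (same settings as step 4, varying the share at the cap) isolates the censoring method, because neither test adjusts for baseline. With 5–20% of placebo at the cap, the linear model ranges from 8 points better to 3 points worse. At 40% it loses 0–7 points, and at 60% it loses 7–14.

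**The case against.** The strongest defence is that the planned test is sound. Capping at 180 minutes gives a well-defined restricted mean, the false-positive rate is correct, and a spike at 180 would fail the normality check and bring in the plan's fallback. That stands as far as validity goes. The fallback, however, only says alternatives will be considered. It names no test, and no transformation removes the pile-up at 180.

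A reader might infer more than the documents support:

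- **That the loss is due to ignoring censoring.** It is mainly due to testing change; steps 4 and 6 show that handling the cap adds a smaller amount, which depends on the distribution.
- **That a standard Cox model adjusted for first-session latency is the remedy.** With model-based standard errors it rejected about 5–10% under no effect, so part of its apparent gain is inflated size. A check with robust standard errors gave 4.3–5.9%.
- **That a missed latency effect ends the mechanistic aim.** The gate applies variable by variable, and five candidates are named. Hypothesis 2.2 also covers calories.
- **That the plan specifies a linear model for this outcome.** The word is used only for Exploratory Aim 3. Linear is a fair inference from the error structures and least-square means.

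Two practical objections also stand and shape the fix. A first session at weeks 4–6 is on treatment, so adjusting for it could absorb part of the drug effect. A baseline-adjusted model could also drop people without a first session, whereas the mixed model uses all available data.

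**Conclusion.** The point holds as a cheap improvement. The planned latency test is valid but weaker than one adjusted for first-session latency, and the coding of full resisters is unspecified. The estimated gain is about 5–20 points of power for adjusted ANCOVA on capped latency and 6–22 for rank ANCOVA, both at nominal size. Those figures rest wholly on the assumptions listed above; the documents supply neither the effect size nor the share at the cap. The direction of the baseline-adjustment gain does not depend on them: under equal variances, (1 + ρ)/2 is below 1 for any correlation short of 1. The consequence is limited to latency and its own mediation test.

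**What to change.** In item 13, Primary Aim 2, write a separate paragraph for latency:

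- Code a participant who does not eat during the window as 180 minutes, never as missing.
- Make the latency test a comparison of second-session latency between arms, adjusted for obesity stratum, first-session latency and an indicator for first-session latency equal to 180. Use rank ANCOVA, or a Cox model censored at 180 minutes with robust standard errors. Name one of these as primary.
- Use that test as the gate to latency mediation.
- Report the difference in restricted mean time to 180 minutes, and use the baseline-adjusted linear coefficient on capped latency as path a for PRODCLIN.
- Use only a pre-treatment first session as the covariate. Treat one held at weeks 4–6 as a missing baseline, for example by mean imputation with a missing indicator, so that no one is dropped.
- Keep the planned mixed model as a sensitivity analysis.

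The cost is analysis-plan wording and a little more analysis work, with no new data. A rank test or hazard ratio is less directly interpretable than a mean difference, which is why the restricted mean difference should be reported beside it.

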### **SECTION I: RESEARCH PLAN**

1. **Statement of Purpose:** State the scientific aim(s) of the study, or the hypotheses to be tested.

**PRIMARY AIM 1.** To conduct a double-blind, placebo-controlled parallel group study to evaluate the efficacy of naltrexone HCI and bupropion HCI (NB) versus placebo in patients with binge-eating disorder (BED), stratified by obesity status (n=50 per cell, n=200 total).

- *Hypothesis 1.1.* We hypothesize that NB will be superior to placebo for reducing binge eating among patients with BED.
- Hypothesis 1.2. We hypothesize that NB will be superior to placebo for reducing weight among BED patients with obesity.
- Hypothesis 1.3. We will examine whether BED patients with and without obesity derive differential benefit of NB versus placebo on reducing binge eating (i.e., does obesity moderate outcomes).

**PRIMARY AIM 2.** To evaluate correlates and possible mechanisms underlying the effect of NB on binge eating among all participants (n=50 per cell, N=200 total). To evaluate the effect of NB on hypothalamic melanocortin and brain reward systems, eating behavior will be assessed with an established human laboratory paradigm designed to evaluate the ability to resist eating preferred high-caloric food and subsequent over-eating. We will evaluate potential mechanisms including eating peptides (leptin, ghrelin) involved in both homeostatic and hedonic aspects of eating, as well as food craving, mood, hunger, and control over eating.

Hypothesis 2.1. We hypothesize that potential medication-related changes in eating behavior, eating peptides and craving assessed in the laboratory will mediate clinical outcomes during the 12-week treatment period (i.e., rates of binge eating).

Hypothesis 2.2. We hypothesize that NB versus placebo will increase the ability to resist eating preferred high-calorie food, and will reduce overall calorie consumption in patients with BED.

Hypothesis 2.3. We will examine whether BED patients with and without obesity derive differential benefit of NB versus placebo with regards to their ability to resist eating or calories consumed (i.e., does obesity moderate outcomes).

**EXPLORATORY AIM 3**. To assess eating and drinking behavior, food craving, and mood 'in the field' in a subset of participants (n=60).

2. **Probable Duration of Project:** State the expected duration of the project, including all follow-up and data analysis activities.

September 2017 – September 2024

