4. **Research Plan:** Summarize the study design and research procedures using non-technical language that can be readily understood by someone outside the discipline. **Be sure to distinguish between standard of care vs.** research procedures when applicable, and include any flowcharts of visits specifying their individual times and lengths. Describe the setting in which the research will take place.

Overview of Study Design

This single-site, proof-of-concept, clinical trial is a double-blind, placebo-controlled, parallel group study to test the effectiveness of naltrexone + bupropion (NB) pharmacotherapy in BED patients with and without obesity. BED patients with (BMI > 30 and <50) and without obesity (BMI >21.5 and <29.9), will be randomized to NB (32 mg/day naltrexone combined with 360 mg/day bupropion) or placebo (n=50 per cell, n=200 total).

Following eligibility screening and randomization, participants will start a 12-week medication treatment period, a treatment period consistent with other BED medication trials (McElroy et al., 2016). Participants will have four weeks of up-titration: one tablet daily (Naltrexone 8mg/ Bupropion 90mg; 1 week), then two tablets daily (Naltrexone 16mg/ Bupropion 180mg; 1 week), then three tablets daily (Naltrexone 24mg/ Bupropion 270mg; 1 week), to reach the full dose of four tablets daily (Naltrexone 32mg/ Bupropion 360mg). The dosage will continue for the remainder of the 3 months. Medication will be discontinued at the end of 3 months, and patients will then be followed 12-months post-treatment to assess the durability of medication effects. The primary outcome measure is reduction in binge-eating frequency.

To evaluate correlates and mechanisms of NB on eating behavior, assessments will occur in the laboratory and in the field to optimize internal and external validity. Participants will complete human laboratory sessions ("lab sessions") before the start of medication and then during the final week of the 12-week medication period to evaluate the ability to resist eating preferred high-caloric food and subsequent overeating. During the laboratory sessions, we will evaluate potential mechanisms including eating peptides

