### Procedures for Modeling Cue-Induced Eating Behavior.

Each participant will complete two laboratory sessions, the first scheduled prior to starting medication, and the second at the end of medication treatment (week 11-14). This pre-post evaluation by medication group will provide a powerful test of medication effects. Alternatively, if the pre-treatment laboratory session cannot be schedule prior to the beginning of treatment, participants may complete the session around one month of treatment (week 4-6). If we are unable to reschedule at the HRU/CSRU, the lab session will take place at [name] in dedicated lab rooms in [name] research space. Our previous eating study (HIC# 0909005678, [name]) took place in this setting and was very successful. There will be no blood collected throughout the lab session if it occurs at [name], but baseline samples will be obtained on the 4th Floor YCCI unit. All other lab procedures will remain the same. Participants will not be excluded from the treatment study if they are not willing to do the lab sessions, or if they are not able to be scheduled for the lab sessions. Research procedures related to the treatment study (e.g., blood draws for liver function, lipids, and metabolic function) will still be drawn if lab sessions are not completed.

Laboratory sessions will be completed at the Hospital Research Unit (HRU) of the Yale Center for Clinical Investigation (YCCI) located at Yale-New Haven Hospital or the Church Street Research Unit (CSRU) at [name]. Participants will be instructed not to eat past 10:00pm the night before the laboratory session. They will arrive at the HRU/CSRU at 7:30am. At the start of the lab session, participants will have an IV cannula inserted and complete the baseline assessments listed in **Table 1**. Participants will then receive breakfast to standardize time since last food consumption. Breakfast will be a breakfast bar that is approximately 150 calories provided by the Research Team. Participants will then be food deprived for the next 3 hours. Based on our prior work, this length of food deprivation is sufficient to increase food craving. After 3 hours of food deprivation, participants are presented with preferred high-caloric snacks. Participants will be asked to take their study medication prior to the second lab session. Scheduling is limited to HRU/CSRU and participant availability.

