Supplementary analysis: Retention, compliance, and sex. These analyses will provide insight into outcomes which will help us to consider directions for future research. We plan to explore whether medication compliance [plasma bupropion, naltrexone, 6-beta-naltrexol levels, pill counts], and length of time in treatment influenced our primary outcomes. Analyses described earlier will be repeated separately with a) counts of pills taken as a covariate, and b) length of time in treatment as a covariate. In participants taking active medication we will conduct a logistic regression examining area under the curve for the three plasma medication levels as a predictor of our primary outcome (frequency of binge eating) and as predictor of treatment-related change in potential mechanisms. Associations between plamsa medication levels and changes in mechanisms will provide an indication that medication is driving the change in the predictor variable. We also plan to evaluate whether sex moderates medication effects on all study outcomes. Analyses described in D.7.3. will be repeated with sex as between subject variable. We will also explore effects related to laboratory outcomes assessing estrogen and progesterone levels as covariates.

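### Aim 2's 12-week mediation test cannot tell a laboratory mechanism from a laboratory response to reduced binge eating, yet a significant result counts as support for Hypothesis 2.1

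*Combined protocol and SAP*

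**What the plan says.** Hypothesis 2.1 (Section I, item 1) is directional: changes in eating behavior, "eating peptides and craving assessed in the laboratory will mediate clinical outcomes during the 12-week treatment period".

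Item 13, Primary Aim 2, sets out the test. A laboratory variable must first show a significant time-by-medication effect. Then "we will then evaluate whether improvement in the variable of interest mediates changes in frequency of binge eating over the 12-week treatment period". The method is a regression of mediator on treatment (path a), a regression of outcome on mediator and treatment (path b), and an asymmetric confidence interval for a\*b. The criterion is that "significant mediation of NB-related changes in lab variables on clinical outcomes (reduction in binge eating frequency) will be considered supportive of our hypothesis". The same paragraph notes that "statistical mediation is not equivalent to causation, and will be sure to appropriately limit our conclusions".

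The timing is given elsewhere:

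- The Overview of Study Design puts the second laboratory session "during the final week of the 12-week medication period". The section on modeling cue-induced eating gives weeks 11 to 14.
- The optional week 4 to 6 session only replaces a missed pre-treatment session.
- Under Measures, the EDE interview is the main method for assessing binge eating and covers the previous 28 days. In Figure 2 it is given at baseline, month 3, and the 6- and 12-month follow-ups.
- Figure 2 also shows the food-craving questionnaires, Power of Food Scale (PFS) and Control of Eating at months 1 and 2, and the EDE-Q at week 2 and months 1 and 2.

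Item 13, Secondary Aims (b), plans exploratory mediation analyses in which questionnaire changes are tested against later binge eating.

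**The concern.** Mediation requires the laboratory variable to change first and binge eating to follow. Here the mediator is read at the end of the outcome window or after it, and nothing in the model represents how binge eating had already changed. If the drug reduces binge eating by some other route, and fewer binges lead to less craving, lower intake or altered peptides in the laboratory, both paths are non-zero and the rule is met.

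What is at stake is the mechanistic conclusion of a primary aim: Hypothesis 2.1 could be counted as supported when the laboratory change is a consequence. The Aim 1 efficacy tests and the Hypothesis 2.2 treatment effects on laboratory variables do not depend on this step.

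**Working it through.** The plan gives no effect size, power or mediator-outcome correlation, so it has no figure to reproduce.

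**1. Timing.** Share of the 28-day window already past at the laboratory session = (lab week − (EDE week − 4)) / 4. Month 3 is taken as week 12, with week 14 as a late case.

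- EDE week 12, lab week 11: (11 − 8)/4 = 75%. Lab weeks 12 to 14: 100%.
- EDE week 14, lab week 11: (11 − 10)/4 = 25%.

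In none of these combinations does the session precede the window. Aim 2 does not name the binge-eating instrument. Using the EDE-Q series instead would not help, because most of its reports come before the session.

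**2. What a\*b shows when the direction is reversed.** Let T be treatment, Y = −dT + e binge eating, and M = rY + √(1 − r²)u the laboratory variable, with e and u standard normal. M mediates nothing. Then a = −rd and b = r, so a\*b = −r²d. With d = 0.5 and r = 0.5 this is −0.125, not zero.

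For the required treatment effect on M, the standard error is √(4/n) and z = rd/√(4/n). The pass rate is P(Z > 1.96 − z), ignoring the negligible other tail.

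| n | r | rd | z | pass rate |
|---|---|---|---|---|
| 200 | 0.3 | 0.15 | 1.06 | 18% |
| 200 | 0.5 | 0.25 | 1.77 | 42% |
| 200 | 0.7 | 0.35 | 2.47 | 70% |
| 124 | 0.3 | 0.15 | 0.84 | 13% |
| 124 | 0.5 | 0.25 | 1.39 | 28% |
| 124 | 0.7 | 0.35 | 1.95 | 50% |

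Here n = 124 is 200 less the 38% upper attrition figure cited in item 12. Path b is rarely the obstacle, so the full rule passes almost as often. Simulation gave about 17%, 39% and 69% at n = 200, and about 13% to 48% at n = 124; repeat runs differed by a few percentage points. If the item 13 Bonferroni correction applied over the five named variables (alpha 0.01), the rates at n = 200 would be about 6%, 20% and 44%.

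**3. Would an earlier mediator be enough?** No. If binge eating has autocorrelation 0.6 (assumed), the earlier M still correlates with later Y at 0.6r = 0.18, 0.30 and 0.42 given treatment. Simulated false support was 11%, 41% and 69%. Adjusting also for binge eating at the mediator visit cut it to about 0.4%, 1.7% and 2.9%, provided the adjuster is measured without error. At r = 0.7, adjuster reliability of 0.8 or 0.6 brought it back to about 25% or 58%.

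**4. What adjustment does to true mediation.** Suppose M acts on Y at every visit with coefficient β, and let s_M and s_Y be the month-to-month stability of M and of residual binge eating. Substituting month-2 values into the month-3 equation gives an adjusted coefficient for month-2 M of β(s_M − s_Y).

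- 0.6 and 0.6: zero. Simulated correct detection was about 2%.
- 0.8 and 0.4: +0.4β. Detection was 39%, 76% and 88% for β = 0.3, 0.5 and 0.7.
- 0.4 and 0.8: −0.4β, the wrong sign. Significant wrong-sign results occurred in 61% to 89% of trials.

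So the adjusted test is not a clean replacement.

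**The case against.** The plan is not careless here. It states the limit of statistical mediation in the same paragraph and promises to restrain its conclusions. Its word is supportive, which is weaker than proof, in a proof-of-concept trial whose Aim 2 seeks correlates and possible mechanisms. Secondary Aims (b) already intends time-ordered mediation on repeated questionnaires. All analyses are to be repeated over the 12-month follow-up, which would put the second session before the outcome. A supplementary analysis adds that "Associations between plamsa medication levels and changes in mechanisms will provide an indication that medication is driving the change in the predictor variable".

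Much of this stands. A reader might infer that the plan ignores time order or causation; it does not. What remains is narrower:

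- The caveat governs wording, while the criterion for a directional hypothesis is unchanged.
- The time-ordered analysis is exploratory and not tied to Hypothesis 2.1.
- The follow-up repeat is not the primary time frame, and "Medication will be discontinued at the end of 3 months", so those outcomes are off drug.
- Plasma levels bear on drug to mechanism, and only in the active arm. The same association would appear if the drug acted on binge eating first.

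A reader might also infer that late timing alone is the fault, or that the adjusted month-2 test should become the sole criterion. Steps 3 and 4 support neither. Earlier measurement without adjustment leaves false support almost as high at the two larger correlations. Adjustment conditions on binge eating that lies on the hypothesised path, so it can miss or reverse true mediation.

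**Conclusion.** The concern holds. It rests on the schedule and the two-regression test: the mediator never precedes the outcome window in the timings examined, earlier binge eating is not modeled, and significance counts as support. That part needs no assumed effect size.

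The rates of about 17% to 69% (n = 200) and 13% to 48% (n = 124) assume a 0.5 SD effect on binge eating, reverse correlations of 0.3 to 0.7, normal data and no true mediation. None of these inputs is in the documents, and one correlation is applied alike to latency, calories, peptides and craving. The rates show that direction is not identified. They should not be read as this trial's false-positive rate, nor as evidence that the reverse path operates.

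The consequence is limited to the mechanistic claim. It is worth correcting before unblinded analysis because the correction uses only data already scheduled.

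**What to change.** 1. In item 13, Primary Aim 2, replace the support criterion. Report change at the second laboratory session against 12-week binge eating as a concurrent association, *consistent with mediation, direction not identified*, and do not count it alone as support for Hypothesis 2.1.
2. For latency, calories, leptin and ghrelin, which are measured only at the laboratory sessions, state that the schedule cannot identify direction within the 12 weeks.
3. For food craving, PFS and Control of Eating, link the time-ordered analysis in Secondary Aims (b) to Aim 2 as a supporting analysis named in advance. Control of Eating must be added to the measures listed there. Test change from baseline to month 2 against month-3 EDE binge frequency. Show it both with and without adjustment for EDE-Q binge frequency at month 2, and add a sensitivity analysis for measurement error in that adjuster.
4. State that the adjusted result is not the sole criterion, and that a null or wrong-sign adjusted result is not evidence against mediation.

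**Cost.** Some extra analysis and no new visits or data. The laboratory variables yield no confirmatory mediation conclusion, and craving is tested by questionnaire rather than in the laboratory, which the wording of Hypothesis 2.1 must reflect. The adjusted analysis is informative only if month-2 change carries a lagged effect. Under assumed partial correlations of 0.2 and 0.3 and a 0.5 SD effect on the mediator, its power is about 77% and 92% at n = 200, and 46% and 72% at n = 124.
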